	Chronic lung disease	ICD-9-CM or ICD-10-CM codes listed in Annex Table 1.7	Baseline and follow-up
	Cigarette smoking	ICD-9-CM or ICD-10-CM codes listed in Annex Table 1.8	Baseline and follow-up
	Diabetes mellitus	ICD-9-CM or ICD-10-CM codes listed in Annex Table 1.9	Baseline and follow-up
	Generalized malignancy	CPT/HCPCS, ICD-10-PCS, ICD-9-PCS, ICD-9-CM or ICD-10-CM codes listed in Annex Table 1.10	Baseline and follow-up
	Hodgkin's lymphoma	ICD-9-CM or ICD-10-CM codes listed in Annex Table 1.11	Baseline and follow-up
	Immunosuppressive medications	PLWH will be considered on immunosuppressive medications if:	Baseline and follow-up

Variable type	Variable	Definition	Measurement period
		1) ≥1 NDC, HCPCS, or ICD-10-PCS code in Appendix Table 6 2) ≥ 1 NDC (using orals only) in Appendix Table 6 where the daily dose is ≥ 20mg or prednisone or prednisone equivalent for a duration of ≥14 consecutive days	
	Leukemia	ICD-9-CM or ICD-10-CM codes listed in Annex Table 1.12	Baseline and follow-up
	Multiple myeloma	ICD-9-CM or ICD-10-CM codes listed in Annex Table 1.13	Baseline and follow-up
	Nephrotic syndrome	ICD-9-CM or ICD-10-CM codes listed in Annex Table 1.14	Baseline and follow-up
	Non-Hodgkin's lymphoma	ICD-9-CM or ICD-10-CM codes listed in Annex Table 1.15	Baseline and follow-up
	Organ transplant	CPT/HCPCS, ICD-10-PCS, ICD-9-PCS, ICD-9-CM or ICD-10-CM codes listed in Annex Table 1.16	Baseline and follow-up
	Sickle cell disease or other hemoglobinopathies	ICD-9-CM or ICD-10-CM codes listed in Annex Table 1.17	Baseline and follow-up
	Hepatitis B	ICD-9-CM or ICD-10-CM codes listed in Annex Table 2.1	Baseline and follow-up
	Hepatitis C	ICD-9-CM or ICD-10-CM codes listed in Annex Table 2.2	Baseline and follow-up
	Annual physical exam	CPT/HCPCS codes listed in Annex Table 3.1	Baseline and follow-up
	Annual influenza vaccine	CPT/HCPCS, ICD-10-PCS, ICD-9-PCS, or NDC codes listed in Appendix Table 7	Baseline and follow-up
	Any pneumonia infection	ICD-9-CM or ICD-10-CM codes listed in Appendix Table 4	Baseline
	Any hospitalization	Evidence of inpatient claims	Baseline and follow-up
	Opportunistic infections	ICD-9-CM or ICD-10-CM codes listed in Appendix Table 14	Baseline and follow-up
	ART adherence	ART use will be identified by NDC codes listed in Appendix Table 2	Baseline and follow-up

Variable type	Variable	Definition	Measurement period

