9.5. Study Size

The planned analyses do not involve hypothesis testing and sample size calculations are not applicable. However, we examined the precision of PCV13 vaccine effectiveness for IPD and all-cause pneumonia among people living with HIV at 36 months and 97 months (which was the maximum follow-up time available from feasibility assessments) after index (Table 2 and Table 3). Komodo Health provided the following information for the precision estimates:

- 175,000 individuals had ≥ 1 inpatient or ≥ 2 outpatient HIV ICD-9-CM or ICD-10-CM code diagnosis codes between January 1, 2014 and December 31, 2021
- 56,000 (32%) of these individuals received PCV13 after their first HIV diagnosis code

The following assumptions regarding incidence and PCV13 VE for IPD and all-cause pneumonia were used:

- IPD incidence among PLWH is 183 cases per 100,000 population [28]
- All-cause pneumonia incidence among PLWH is 5,487 cases per 100,000 population
- VE for IPD due to any serotype ranges from 7.5% to 22.5%
 - Published VE estimates for vaccine type IPD range from 25% to 75% [20]. Because one-third of the adult IPD burden is considered PCV13 type [29], we multiplied this range by 30% to arrive at 7.5% to 22.5%
- VE for all-cause pneumonia ranges from 5% to 15% [30]
- Annual censoring of individuals due to loss to follow-up or death may range between 4% or 10%

Survival and censoring times were simulated assuming exponential distributions. Vaccination status was modelled as a time-varying covariate [31]. Hazard ratios were assumed as $1 - (VE/100)$. Simulations were run 100 to 200 times per scenario. Cox regression models were run on each simulated dataset to estimate the 95% confidence

PFIZER CONFIDENTIAL

intervals (CI) for the log HRs. Means were generated and exponentiated to obtain the 95% CIs for the VEs using $(1 - HR) \times 100$ and used to describe VE precision.

Table 2. Precision of PCV13 vaccine effectiveness estimates for invasive pneumococcal disease

Hypothesized Vaccine Effectiveness (%)	36 months of follow-up			97 months of follow-up		
	Lower 95% confidence interval estimate	Upper 95% confidence interval estimate	Total number of events	Lower 95% confidence interval estimate	Upper 95% confidence interval estimate	Total number of events
Scenario #1 – 4% annual censoring						
7.5	-12	25	837	-5	19	1492
22.5	3	37	817	11	33	1452
Scenario #2 – 10% annual censoring						
7.5	-15	25	766	-6	21	1272
22.5	2	38	752	9	33	1224

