9.7. Data Analysis

Cox proportional hazards models will be used to estimate the hazard ratio (HR) for each outcome comparing vaccinated PLWH with unvaccinated (no PCV13) PLWH. To explore potential changes in VE over time, HRs will also be generated during specific time periods (0-3, 3-5, 5-7 years of follow-up) using piecewise Cox regression models, if there is adequate sample size. All models will be adjusted for time-fixed and time-varying covariates of interest using inverse probability of treatment weighting. The time-fixed covariates of interest include sex, age, payor, SVI, previous pneumonia infection, and hospitalization and will be measured during the baseline period. The time-varying covariates include risk factors for pneumonia (alcoholism, asplenia, asthma, chronic heart disease, kidney, liver, and lung diseases, cigarette smoking, diabetes, immunosuppressive conditions and medications, and sickle cell disease), annual physical exams, annual influenza vaccine, hospitalization, opportunistic infections, ART adherence, annual CD4 and viral load laboratory tests, and an indicator for respiratory virus season.

VE will be calculated as 1 minus the estimated HR for each outcome.

We will conduct two sets of analyses for each outcome. In the first set, we will examine the first event for each outcome and in the second set, all recurrent outcome events during follow-up will be included. In the first set of analyses, unvaccinated (no PCV13) PLWH will be followed from index date until the earliest occurrence of the following: outcome, PCV13 vaccination, death, end of health plan enrollment, or end of study period, and vaccinated PLWH will be followed from 14 days after vaccination date, or index date if vaccinated during the baseline period, until the earliest occurrence of outcome, death, end of health plan enrollment, or end of study period. In the second set of analyses unvaccinated (no PCV13) PLWH will be followed from index date until the earliest occurrence of PCV13 vaccination, death, end of health plan enrollment or end of study period and vaccinated PLWH will be followed from 14 days after vaccination date, or index date if vaccinated during the baseline period, until earliest occurrence of death, end of health plan enrollment, or end of study period.

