ANNEX 1. LIST OF STAND ALONE DOCUMENTS

If there is no document to be listed, delete the table and write “None”.

Number	Document reference number	Date	Title
1	1	January 24, 2023	Annex Code Tables

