### 5.3.2. Covariates

The list of demographic and clinical characteristics considered for descriptive reporting, subgroups and inclusion as covariates in models for generating the propensity scores are provided in Table 5.3. The Komodo Health database will be source of all variables.

Patients will be considered to have a comorbidity or hospitalization during baseline if there was evidence of a diagnosis at any time during the baseline period. Evidence of comorbidities or hospitalization during follow-up will be considered as new diagnoses. Once diagnosed, patients will be considered diagnosed for the remainder of their follow-up. ART adherence during baseline and follow-up will be updated every 6 months (180 days) based on the data collected in that previous timeframe. For baseline annual physical exam and annual influenza vaccine, patients will be considered adherent (coded as 'Yes') if there was evidence of these events at any time during the baseline period. During the follow-up, patients will be considered adherent up to 365 days after the last event date.

For annual CD4 and viral load laboratory tests during baseline and follow-up, patients will be coded as 'Yes' up to 365 days after the last event date. For respiratory virus season during follow-up, patients will be coded as 'Yes' if the observation time is in October, November, December, January, February, March or April.

The baseline period for the assessment of covariates is the six months prior to the index date, i.e., no data prior to six months will be included.

Covariates used at baseline only will be considered time-fixed confounders. Covariates additionally or only used during follow-up will be considered time-varying confounders.

Categories may be collapsed, or covariates may be excluded from the propensity scores if models fail to converge.

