Asthma	ICD-9-CM or ICD-10-CM codes listed in Protocol Annex Table 1.3 Yes, No	Descriptive, covariate	Baseline and follow-up
Diabetes mellitus	ICD-9-CM or ICD-10-CM codes listed in Protocol Annex Table 1.9 Yes, No	Descriptive, covariate	Baseline and follow-up
Generalized malignancy	CPT/HCPCS, ICD-10-PCS, ICD-9-PCS, ICD-9-CM or ICD-10-CM codes listed in Annex Table 1.10	Descriptive, covariate	Baseline and follow-up
Immunosuppressive medications	PLWH will be considered on immunosuppressive medications if: 1) ≥1 NDC, HCPCS, or ICD-10-PCS code in Appendix Table 7.7	Descriptive, covariate	Baseline and follow-up

	2) ≥ 1 NDC (using oral only) in Appendix Table 7.7 where the daily dose is ≥ 20mg or prednisone or prednisone equivalent for a duration of ≥14 consecutive days Yes, No		
Leukemia	ICD-9-CM or ICD-10-CM codes listed in Protocol Annex Table 1.12	Descriptive, covariate	Baseline and follow-up
Multiple myeloma	ICD-9-CM or ICD-10-CM codes listed in Annex Table 1.13	Descriptive, covariate	Baseline and follow-up
Nephrotic syndrome	ICD-9-CM or ICD-10-CM codes listed in Protocol Annex Table 1.14 Yes, No	Descriptive, covariate	Baseline and follow-up
Non-Hodgkin's lymphoma	ICD-9-CM or ICD-10-CM codes listed in Protocol Annex Table 1.15	Descriptive, covariate	Baseline and follow-up
Organ transplant	CPT/HCPCS, ICD-10-PCS, ICD-9-PCS, ICD-9-CM or ICD-10-CM codes listed in Protocol Annex Table 1.16	Descriptive, covariate	Baseline and follow-up
Sickle cell disease or other hemoglobinopathies	ICD-9-CM or ICD-10-CM codes listed in Protocol Annex Table 1.17 Yes, No	Descriptive, covariate	Baseline and follow-up
Hepatitis B	ICD-9-CM or ICD-10-CM codes listed in Protocol Annex Table 2.1 Yes, No	Descriptive, covariate	Baseline and follow-up
Hepatitis C	ICD-9-CM or ICD-10-CM codes listed in Protocol Annex Table 2.2 Yes, No	Descriptive, covariate	Baseline and follow-up
Cigarette smoking	ICD-9-CM or ICD-10-CM codes listed in Protocol Annex Table 1.7 Yes, No	Descriptive, covariate	Baseline and follow-up
Annual physical exam	CPT/HCPCS codes listed in Protocol Annex Table 3.1 Yes, No	Descriptive, covariate	Baseline and follow-up
Annual influenza vaccine	CPT/HCPCS, ICD-10-PCS, ICD-9-PCS, or NDC codes listed in Appendix Table 7.8 Yes, No	Descriptive, covariate	Baseline and follow-up
Any pneumonia infection	ICD-9-CM or ICD-10-CM codes listed in Appendix Table 7.4 Yes, No	Descriptive, covariate	Baseline

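### SAP Table 5.3 points cigarette smoking to the chronic lung disease code list (Annex Table 1.7, not 1.8); read literally, the weights would not adjust directly for smoking

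*SAP*

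**What the plan says.** SAP Table 5.3 gives the operational definition of each covariate. Two of its rows, chronic lung disease and cigarette smoking, carry the same definition: "ICD-9-CM or ICD-10-CM codes listed in Protocol Annex Table 1.7 Yes, No". Only the row label tells them apart.

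Protocol Table 1 (section 9.3) separates the two. Chronic lung disease is defined by "ICD-9-CM or ICD-10-CM codes listed in Annex Table 1.7" and cigarette smoking by "ICD-9-CM or ICD-10-CM codes listed in Annex Table 1.8".

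Table 5.3 is more than background. SAP 5.3.2 says that the variables considered for descriptive reporting, subgroups and "inclusion as covariates in models for generating the propensity scores are provided in Table 5.3". Protocol 9.7 names lung disease and smoking as distinct time-varying risk factors for pneumonia: "chronic heart disease, kidney, liver, and lung diseases, cigarette smoking, diabetes".

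The annex is a stand-alone file, listed in Protocol Annex 1 as "Annex Code Tables", and is not reproduced in either document.

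**The concern.** The SAP is the document from which the covariates will be programmed. Protocol 9.7 leaves the detailed methodology to it and allows it to depart from the protocol's outline, so a programmer who sees the two differ could reasonably follow the SAP.

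A variable called smoking but built from the lung disease list would leave smoking without direct adjustment. The SAP plans no dependable second route. Smoking is measured at baseline and during follow-up, which makes it time-varying under SAP 5.3.2. Under SAP 5.8.4, time-varying covariates enter the weight denominators only. Under SAP 5.8.7, the covariates carried into the outcome model are the time-fixed ones. SAP 5.8.5 allows a covariate that is still imbalanced after weighting to be added to the outcome model, but that judgement would be made on the mislabelled variable.

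Weights are built separately for each outcome, for first and recurrent events, and again in each subgroup, so one wrong code list would carry through all the weighted results.

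**Working it through.** **1. Compare the annex references.**

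| Covariate | Protocol Table 1 | SAP Table 5.3 |
|---|---|---|
| Chronic lung disease | 1.7 | 1.7 |
| Cigarette smoking | 1.8 | **1.7** |
| Diabetes mellitus | 1.9 | 1.9 |

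The SAP cites Annex Tables 1.1 to 1.7 and 1.9 to 1.17, cites 1.7 twice, and never cites 1.8. Its other references to the 1.x tables, and those to 2.1, 2.2 and 3.1, match the protocol.

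**2. Could the annex have been renumbered, or the definition changed on purpose?** Renumbering would shift the later tables, but the SAP's diabetes row still reads "ICD-9-CM or ICD-10-CM codes listed in Protocol Annex Table 1.9 Yes, No", as in the protocol. Neither amendment log records a change to the smoking definition, and no other part of the SAP defines smoking.

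**3. What does a literal reading do to the models?** A design matrix with an intercept and the same indicator entered twice has 3 columns and rank 2. The second copy adds no information: lung disease is adjusted for once, and smoking is not directly adjusted for. The models affected are the denominators of the treatment weights and of the censoring weights, which SAP 5.8.4 builds in the same way. The numerators use time-fixed covariates only and do not change.

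**4. What does it do to the tables?** The smoking rows of the characteristics table (SAP 5.8.9) and of the standardized differences (SAP 5.8.5) would repeat the lung disease rows.

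**5. How large could the bias be?** The plan has no figure to reproduce. It gives neither smoking prevalence by vaccination status nor a rate ratio for smoking, so the inputs below are assumptions. With true VE of zero and an omitted binary confounder:

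apparent VE = 1 − [1 + p1(RR − 1)] / [1 + p0(RR − 1)]

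Here p0 is smoking prevalence in unvaccinated time, p1 is prevalence in vaccinated time, and RR is the rate ratio for smoking.

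| RR | p0 | p1 | Ratio | Apparent VE |
|---|---|---|---|---|
| 1.5 | 0.40 | 0.35 | 1.175/1.200 = 0.979 | +2.1% |
| 1.5 | 0.40 | 0.30 | 1.150/1.200 = 0.958 | +4.2% |
| 2 | 0.40 | 0.35 | 1.350/1.400 = 0.964 | +3.6% |
| 2 | 0.40 | 0.30 | 1.300/1.400 = 0.929 | +7.1% |
| 1.5 or 2 | 0.40 | 0.40 | 1.000 | 0 |
| 1.5 | 0.35 | 0.40 | 1.200/1.175 = 1.021 | −2.1% |
| 2 | 0.35 | 0.40 | 1.400/1.350 = 1.037 | −3.7% |

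For scale, Protocol 9.5 assumes a VE of 5% to 15% for all-cause pneumonia.

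The formula allows no control through correlated covariates. It also assumes that correct coding would remove all confounding by smoking. Both assumptions push the figures up.

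**The case against.** The strongest reply is that this is a one-digit slip. The row is labelled cigarette smoking, it sends the reader to the protocol's own annex, and the protocol has the right number. Protocol 9.6 says that the analyses follow the final protocol. The SAP has other loose references nearby, such as broken cross-references in 5.8.10 and 5.8.11. Nothing shows that any program used the wrong list. All of this stands, and it bears on how likely harm is. It does not remove the contradiction from an operative definition.

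A reader might also infer more than the documents support:

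- **Every VE estimate is confounded by smoking.** Crude VEs are unadjusted whichever table is cited. Weighted VEs would still adjust for lung disease, asthma, heart disease, alcoholism and hospitalization, which may capture part of the smoking effect.
- **Every propensity model is affected.** Only the denominator models are.
- **Lung disease would be over-adjusted.** An exact copy carries no additional weight.
- **The SAP would let the duplicate be dropped unseen because it is collinear.** SAP 5.3.2 allows covariates to be excluded when models fail to converge and says nothing about collinearity. Identical counts and identical standardized differences in two rows would also be conspicuous to anyone comparing them.
- **VE is inflated by 2 to 7 points.** That range comes from assumed inputs that all run in one direction. The documents fix neither the size nor the sign. Under Protocol 9.8, absence of a code counts as absence of the characteristic, so smoking coded from 1.8 would also adjust imperfectly, and the bias due to the slip alone is smaller than the formula suggests.

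The negative controls in SAP 5.8.8 might pick up residual confounding, but they would not identify this cause.

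**Conclusion.** The mismatch is certain: SAP Table 5.3 and Protocol Table 1 name different code tables for smoking, and the SAP uses the lung disease table twice. It is most likely clerical. The consequence is conditional. If the SAP row was programmed literally, smoking is not directly adjusted for in the weight denominators behind the weighted VE estimates, and the rows labelled smoking describe lung disease.

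The size and sign of any resulting bias cannot be determined from the documents. Under the stated assumptions (rate ratio 1.5 to 2), it runs from about +2 to +7 points when smoking is less common in vaccinated time, is zero when prevalence is equal, and is about −2 to −4 points when 40% smoke in vaccinated time against 35% in unvaccinated time. Partial control through correlated covariates would shrink these figures.

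The conclusion also rests on the annex tables holding what the protocol's labels say, since the annex was not available to check. The row should be corrected because it defines a named confounder and the correction is trivial. The documents do not show that any result is wrong.

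**What to change.** Change the cigarette smoking row of SAP Table 5.3 to Protocol Annex Table 1.8. Each of Annex Tables 1.1 to 1.17 is then cited once, and the SAP agrees with Protocol Table 1.

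Before the weights are built, confirm that the programmed smoking variable uses the 1.8 list. A quick test is whether the smoking and chronic lung disease counts are identical.

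If weights already exist, make the same check. Rerun them, with the weighted estimates and the descriptive and balance tables, only if the 1.7 list was used.

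The cost is one digit in the SAP and one programming check, plus a rerun only in that last case.

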### 5.3.3. Negative Controls

**Table 5.4 List of Negative Control Variables**

Variable	Operational Definition	Role	Time of Use
Recombinant zoster vaccine (RZV; Shingrix, GlaxoSmithKline)	NDC and CPT codes listed in Appendix Table 7.10	Negative control exposure	Follow-up
May include, but not limited to, candidiasis infection, all-cause diarrhea and accidental injury	ICD-9-CM and ICD-10-CM codes listed in Protocol Annex Table 4.1  Candidiasis infection: evidence of an antifungal treatment within 7 days of outpatient candidiasis ICD-9-CM or ICD-10-CM codes will be explored. NDC and CPT codes listed in Appendix Table 7.13	Negative control outcomes	Follow-up

### 5.4. Data Sources

*The source of data for the VE study will be health care administrative claims and HIV-laboratory data provided by Komodo Health. Komodo Health uses artificial intelligence and data analytics to combine and link patient-level information from more than 150 payers in the United States, including Medicare, Medicaid, and Commercial plans. Currently, Komodo Health has patient-level data on approximately 325 million individuals and these data include inpatient and outpatient claims, pharmacy dispensing claims, provider specialty claims, and mortality information.*

*Komodo Health will provide administrative claims available during January 1, 2014 through September 30, 2022 for individuals who have at least one ICD-9-CM or ICD-10-CM code related to HIV (Appendix Table 7.1) or at least one antiretroviral (ART) medication dispensed (Appendix Table 7.2).*

### 5.5. Treatment Labels

Information on PCV13 vaccination status will continue to be collected on and after index date and will therefore be treated as a time-varying exposure. PLWH in the study will be assigned to 'PCV13 Vaccinated' or 'PCV13 Unvaccinated' according to their vaccination status by each person-time record during the follow-up. Individuals will be considered vaccinated from 14 days after their PCV13 vaccination date till the remainder of their follow-up.

National Drug Codes (NDC) and Current Procedural Terminology® (CPT) codes used to identify PCV13 receipt are listed in Appendix Table 7.3.

## 5.6. Sample Size and Power Calculations

*The planned analyses do not involve hypothesis testing and sample size calculations are not applicable. However, we examined the precision of PCV13 vaccine effectiveness for IPD and all-cause pneumonia among people living with HIV at 36 months and 97 months (which was the maximum follow-up time available from feasibility assessments) after index. This was conducted for the 175,000 individuals expected in the overall analysis (Protocol Section 9.5) and for varying potential subgroup sizes (Section 5.2.3).*

## 5.7. Missing Data

No imputation for missing values will be performed. Subject to patient counts (Section 5.8.3), missing or ‘unknown’ values will be reported and analyzed as separate categories and included in the totals.

## 5.8. Statistical Methodology and Analyses

### 5.8.1. General Considerations

Descriptive statistics will be used to summarize variables. For categorical variables, the frequency and percentage of patients in each category will be presented. Percentages will be based on the total number of relevant patients, including those with ‘unknown’ or missing values. For continuous variables, data will be presented as means, standard deviations, medians, 25th and 75th percentiles, minimums and maximums. Continuous variables may be additionally categorized and analyzed as categorical variables.

No statistical hypotheses are specified and there will be no correction for multiple comparisons.

Time in years between two dates will be calculated as (end date – start date) + 1, divided by 365.25, unless otherwise specified.

All data analysis will be conducted in R, version 4.1.3 or later (R Foundation for Statistical Computing, Vienna, Austria).

